Abnormal Pregnancy Outcomes (e.g. spontaneous abortion, fetal death, stillbirth, congenital anomaly, ectopic pregnancy)	Within 15 calendar days of becoming aware of the event(s)	By a secure means, as agreed by the Parties, on a Serious Adverse Event Form.
Lack of Effect (with or without a suspected adverse reaction), must be reported as an SAE.	Within 15 calendar days of becoming aware of the event(s).	By a secure means, as agreed by the Parties, on a Serious Adverse Event Form.
Product Quality Complaints	Within 3 business days of becoming aware of the event(s)	By a secure means, as agreed by the Parties.
Non-Serious Adverse Event* (*Not meeting other listed 3 business day reporting criteria e.g. AESI)	Annually and in final study report.	Recorded in CRF and reported annually and in final study report.
Follow-up information	Transmitted within the same timeframes as above i.e. if initial report was required to be submitted within 15 calendar days, follow-up information shall be submitted within the same timeframe.	Transmitted via same method as above i.e. if initial method of transmission was on an SAE form, follow-up information shall be transmitted in the same manner.

Janssen SAE/Pregnancy Notifications	
TO: [contact]
 
Please note the underscores (_) in the email name this is critical to highlight as if its missing then the SAE will fail to transmit.
 
CC: Janssen SRS/SRP and Clinical Project Scientist

-------------------------------------	--

Janssen PQC:	[contact] CC: Janssen SRP/CPS
Janssen [contact]

Statistical analysis

A power analysis resulted in the two possible sample sizes as shown below:

*An a priori power analysis was performed using g*power to estimate sample size for a paired sample t-test. Using a small effect size ($d=.2$), power of 80% (alpha of .05), the desired sample size is 199.*

*An a prior power analysis was performed using g*power to estimate sample size for a paired sample t-test. Using a medium effect size ($d=.5$), power of 80% (alpha of .05), the desired sample size is 34.*

Per literature review, studies with educational interventions in patients with SSD had sample sizes ranging from 20s to several hundreds. None of the studies provided information on power analysis calculations or how sample size was obtained. Given that we will not have access to 200 patients with schizophrenia spectrum disorders at the study site within the time frame of the study, we have chosen to use the former power analysis.

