To assess changes in knowledge and attitudes, a paired samples t-test will be completed on pre-intervention and post-intervention scores for the KAST and ATT. Demographic data will be analyzed using regression analysis.

Data Collection and Storage

Each study participant will be given an arbitrary study identification number. The study ID number will be used on all data collected for the purposes of this study. All assessments and questionnaires for this study will be entered using a tablet into the REDCAP system, a secure and HIPAA compliant web-based system provided through LSUHSC- New Orleans for data collection. Permission to access the project's Research Electronic Data Capture (REDCAP) program must be approved by an investigator or study coordinator. Participants and linking study identification numbers will be kept in a database outside of the REDCAP system on the LSUHSC-NO secure network drive in a folder that can only be accessed by individuals given permission by the primary investigator and study coordinator. This information will also be protected by a password only known to the study personnel. Informed consent forms will be kept in individual participant files which will be in locked file cabinets in a locked door.

Data extracted from the medical records will also be given an arbitrary study ID. This data will be collected using the REDCAP system. To track patient data that has been retrieved, a separate database will be kept on the LSUHSC-NO network drive linking the patient's medical

requisition number with the arbitrary study ID. This database will also be protected by a password only known to study personnel.

After the data has been analyzed and the study closed, data will be destroyed in compliance with LSUHSC-NO Institutional Review Board requirements.

Citations

1. Coleman, K. J., Stewart, C., Waitzfelder, B. E., Zeber, J. E., Morales, L. S., Ahmed, A. T., Ahmedani, B. K., Beck, A., Copeland, L. A., Cummings, J. R., Hunkeler, E. M., Lindberg, N. M., Lynch, F., Lu, C. Y., Owen-Smith, A. A., Trinacty, C. M., Whitebird, R. R., & Simon, G. E. (2016). Racial-Ethnic Differences in Psychiatric Diagnoses and Treatment Across 11 Health Care Systems in the Mental Health Research Network. *Psychiatric services (Washington, D.C.)*, 67(7), 749–757. <https://doi.org/10.1176/appi.ps.201500217>

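### The sample-size statement adopts the 199-patient calculation in the same sentence that says 200 patients cannot be reached

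*Protocol*

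**What the plan says.** The Statistical analysis section introduces the calculations with "A power analysis resulted in the two possible sample sizes as shown below". They appear in this order:

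1. "Using a small effect size ($d=.2$), power of 80% (alpha of .05), the desired sample size is 199"
2. "Using a medium effect size ($d=.5$), power of 80% (alpha of .05), the desired sample size is 34"

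After a remark on sample sizes in the literature, the section gives its reason for choosing, "Given that we will not have access to 200 patients with schizophrenia spectrum disorders at the study site", and ends the same sentence with "within the time frame of the study, we have chosen to use the former power analysis".

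The analysis to be powered follows directly: "a paired samples t-test will be completed on pre-intervention and post-intervention scores for the KAST and ATT". The Study Aims/Objectives section names the post-intervention KAST and ATT scores as the primary endpoints. Neither that section, nor the eligibility criteria, the Phase 2 procedures or the recruitment timeline in Phase 3 gives a planned number of patients.

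**The concern.** The reason and the choice point in opposite directions. A shortage of patients is a reason to reject the larger calculation, yet the word used selects it. Read literally, the Protocol commits to 199 patients, which it says are not available, and to 80% power for a small effect. Read by its reasoning, it commits to 34 patients and 80% power for a medium effect.

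This is the Protocol's only statement of sample size. As it stands, an ethics board, the funder or a later reader cannot tell when enrolment is complete or what effect the primary comparisons can detect. If about 34 patients are enrolled while 0.2 remains the adopted effect, a non-significant KAST or ATT result could be taken as evidence against a small effect when the trial had little chance of finding one.

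A second, smaller point is that the target is not expressed as patients with both a Day 1 and a Day 4 score, which is what a paired t-test counts.

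**Working it through.** **Inputs, all from the Statistical analysis section.** Paired t-test; d = 0.2 with n = 199; d = 0.5 with n = 34; power 80%; alpha 0.05. Sidedness is not stated. Two-sided is inferred below because it reproduces both figures and one-sided does not.

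**Formula.** For n pairs and a standardised mean paired difference d, the test statistic follows a noncentral t distribution with n − 1 degrees of freedom and noncentrality λ = d√n. With c = t(0.975, n − 1), power = P(T > c) + P(T < −c).

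**Step 1: reproduce the stated sizes.**

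| d | n | c | λ = d√n | Power |
|---|---|---|---|---|
| 0.2 | 198 | 1.972 | 0.2 × √198 = 2.814 | 0.7997 |
| 0.2 | 199 | 1.972 | 0.2 × √199 = 2.821 | 0.802 |
| 0.5 | 33 | 2.037 | 0.5 × √33 = 2.872 | 0.795 |
| 0.5 | 34 | 2.035 | 0.5 × √34 = 2.915 | 0.808 |

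The smallest sizes reaching 80% are 199 and 34, as stated. One-sided testing would give 156 and 27, which do not match. The calculations are therefore sound, and which one is the former is not in doubt.

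**Step 2: compare the two readings of the sentence.**

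| Reading | Target n | Effect at 80% power | Fits the stated shortage of patients? |
|---|---|---|---|
| Literal (former) | 199 | 0.2 | No |
| By the reason given (latter) | 34 | 0.5 | Yes |

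Size ratio: 199 / 34 = 5.9. Effect ratio: 0.5 / 0.2 = 2.5.

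**Step 3: what 34 pairs can detect.** At n = 34 and d = 0.2, λ = 0.2 × √34 = 1.166 and c = 2.035, giving power 0.205. The smallest effect with 80% power at n = 34 is d = 0.495.

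**Step 4: if 34 means enrolled rather than paired.** The Protocol gives no loss rate, so 10% to 20% before Day 4 is assumed here.

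- 10% loss: 34 × 0.90 = 30.6, about 31 pairs; λ = 0.5 × √31 = 2.784; power 0.768 at d = 0.5.
- 20% loss: 34 × 0.80 = 27.2, about 27 pairs; λ = 0.5 × √27 = 2.598; power 0.706 at d = 0.5.

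**The case against.** The best defence is that this is a one-word slip any careful reader would correct. The sentence itself rules out 200 patients and only one alternative is listed. No endpoint, procedure or analysis changes, and neither power calculation is wrong. It is fair to call the fault an internal contradiction rather than an error of arithmetic. But the word falls on the only place where the trial's size is fixed. The intended reading can be inferred; the document does not confirm it.

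It can also be said that the Protocol has no rule for interpreting a null result and does not tie the end of recruitment to a number. That is true, and the misreading of a null result is a risk rather than something the text commits to. The narrower consequence stands without it: there is no unambiguous target size or detectable effect.

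The pairs point is the weakest part. A sample size computed for a paired t-test is by definition a count of pairs. Several features also limit loss: both assessments are planned during the inpatient stay, missed sessions are postponed, patients too unwell to complete the assessments are excluded, and payment comes at discharge. An attrition allowance may sit in a SAP that is not at hand. The 10% to 20% range is an assumption. What remains is that 34 leaves almost no slack, since 33 pairs already fall below 80%, so it is worth saying what the number counts. The main conclusion does not depend on this.

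**Conclusion.** The concern holds, and the correction is needed. As written, the Protocol adopts a size of 199 that it declares out of reach, together with 80% power for d = 0.2 that it will not have. The reason given supports only the second calculation, 34 patients and d = 0.5. At that size power is 80.8% for 0.5 and 20.5% for 0.2.

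These figures assume a two-sided 5% test, inferred from the match in both calculations, and 34 complete pairs. That 'latter' was intended is the only reading consistent with the stated reason, but the sponsor must confirm it. The 71% to 77% range for 27 to 31 pairs rests on an assumed loss and is secondary.

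**What to change.** Once the sponsor has confirmed the intended target, replace 'former' with 'latter' in the Statistical analysis section and add a statement such as: *Target 34 participants with both Day 1 and Day 4 scores; this gives about 80% power (two-sided alpha 0.05) for a standardised mean paired difference of 0.5; power for 0.2 is about 20%, so a non-significant result does not exclude a small effect.*

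If the sponsor did mean 199, the remark that 200 patients are not available has to be reconciled with that target instead.

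The cost is a one-sentence protocol correction with no change to procedures or analysis. The stated detectable effect becomes 0.5 instead of 0.2, which is less favourable but is what a trial of 34 can support.
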